6.6.4 Dose Escalation Rules

The criteria for dose escalation are based on the occurrence of AEs and/or DLTs during the DLT period in evaluable participants in each cohort. The DLT assessment period of 3 weeks (Part A) or 4 weeks (Part B) after the start of M3814 treatment allows an evaluation of acute toxicity. M3814 dose escalation will not proceed to the next dose level until the SMC has decided to escalate. Moreover, RT and the combination of RT and M3814 and avelumab can also give rise to later toxicities, especially radiation toxicities. A 30-day and 90-day Safety Follow-up will be performed in all participants in both Parts (A and B) of the study. Once available, these data, alongside with emerging safety, PK, and Pd data from the ongoing clinical projects involving M3814, will also guide subsequent dose escalation and the establishment of the RP2D. Furthermore, RT Safety Follow-up Visits will be performed in all participants in Part B 1 month (Short-Term RT Safety Follow-up), 3 months (Mid-Term RT Safety Follow-up), and 12 months (Long-Term RT Safety Follow-up, by telephone) after the last RT treatment, to assess any late RT toxicity. These data will be considered in determining the safety profile of the treatment combination.

Dose Escalation Part A (M3814 + avelumab 800 mg Q2W)

A Bayesian two-parameter logistic regression model with overdose control will be used to assist the SMC with dose selection during the Part A dose escalation. Cohorts of at least 3 participants each will be treated at the same dose level of M3814 (starting dose: 100 mg tablet formulation, BID) in combination with avelumab. On the day of avelumab administration, M3814 can be given prior to the start or just after the end of avelumab infusion. The model incorporates available clinical data and observed data from each completed cohort (and data from all previous cohorts) to provide a recommended dose for the next cohort. A preselected set of

acceptable doses are considered by the model as described in Table 13; however, doses which are not part of the prespecified set may be chosen as well, as long as they are within the prespecified dose ranges based on considerations of safety, PK, and Pd data generated in previous cohorts, and the model. Yet, if the sample size in Part A has to be increased to accommodate additional dose levels, a protocol amendment with rationale will be submitted prior to implementation. Moreover, the SMC or the Sponsor may decide to stop the ascending dose process as soon as the first dose level is declared safe and tolerable. This decision will be based on safety, PK and/or Pd data available during the first cohort and/or emerging data from the clinical studies which are currently evaluating the human pharmacology, safety and tolerability of M3814. It is anticipated that 6 to 30 participants (3 to 6 participants at each dose level) may be needed.

Table 13 Example of Possible Dose Levels of M3814 in Combination with Avelumab (Part A)

Dose Level	M3814 Schedule (mg; BID)	Total Daily M3814 Dose (mg)	Avelumab Schedule ^a	Avelumab Dose (mg)
-1 ^b	50	100	Q2W	800
1°	100	200	Q2W	800
2	200	400	Q2W	800
3	400	800	Q2W	800
4	800	1600	Q2W	800

BID=twice daily, DLT=dose-limiting toxicity, IV=intravenous, Pd= pharmacodynamic, PK=pharmacokinetic, Q2W=once every 2 weeks, SMC=Safety Monitoring Committee.

Dose escalation will be based on the presence/absence of DLTs and study intervention-related clinically relevant adverse events during the DLT period. Available PK and Pd data will also be taken into consideration.

- a Avelumab will be administered Q2W as an IV infusion over 1 hour, starting on Day 1, at a fixed dose of 800 mg in all dose levels.
- b Dose Level -1 can be evaluated upon decision of the SMC.
- c Dose Level 1 is the starting dose.

Dose Escalation Part B (M3814 + radiotherapy + avelumab 800 mg Q2W)

Similar to Part A, a separate Bayesian two-parameter logistic regression model with overdose control will be used in Part B to assist the SMC. Following completion of the first cohort (Dose level 1) in Part A, participants with selected advanced or metastatic will be enrolled in the first cohort and will receive M3814 tablet formulation, QD, to be given 1.5 hours (± 30 minutes) prior to the start of RT. On the day of avelumab administration, M3814 can be given at any time after the end of the avelumab infusion. Assuming that the first starting dose level in Part A is declared safe and tolerable, the starting dose of M3814 in the first cohort of participants will be 100 mg total daily dose (i.e. 2-fold lower than in Part A). However, this starting dose might be adjusted by the SMC, based on safety, PK, and Pd data generated during the first dose level in Part A and/or emerging data from the ongoing clinical studies involving M3814 and RT that may justify another starting dose.

Based on the occurrence of AEs and/or DLTs, the SMC will decide if the dose can be escalated or de-escalated to the next dose level. The model will incorporate CCI clinical data and observed data from each completed cohort to provide a recommended dose for the next cohort.

A preselected set of acceptable doses are considered by the model (Table 14), however, doses which are not part of the prespecified set may be chosen as well, as long as they are within the prespecified dose ranges based on considerations of safety, PK, and Pd data generated in previous cohorts, and the model. Yet, if the sample size in Part B has to be increased to accommodate additional dose levels, a protocol amendment with rationale will be submitted prior to implementation. It is anticipated that 6 to 24 participants (3 to 6 participants at each dose level) may be needed.

Table 14 Example of Possible Dose Levels of M3814 in Combination with Radiotherapy and Avelumab (Part B)

Dose Level	M3814 Schedule ^a (mg; QD)	Total Daily M3814 Dose (mg)	Radiotherapy Schedule ^b	Avelumab Schedule ^c	Avelumab Dose (mg)
-1ª	50	50	30 Gy as 3 Gy × 10 (5 F/W)	Q2W	800
1 ^e	100	100	30 Gy as 3 Gy × 10 (5 F/W)	Q2W	800
2	200	200	30 Gy as 3 Gy × 10 (5 F/W)	Q2W	800
3	300	300	30 Gy as 3 Gy × 10 (5 F/W)	Q2W	800

DLT=dose-limiting toxicity, F/W=fractions/week, IV=intravenous, Pd= pharmacodynamic, PK=pharmacokinetic, Q2W=once every 2 weeks, QD=once daily, RT=radiotherapy, SMC=Safety Monitoring Committee.

Dose escalation will be based on the presence/absence of DLTs and study intervention-related clinically relevant adverse events during the DLT period. Available relevant safety data which occur during the RT Safety Follow-up at 1, 3, and 12 months. Available PK and Pd data will also be taken into consideration.

- M3814 will be administered once a day for 5 days followed by 2 days off for 10 days in total (i.e. to the same schedule as RT).
- b Radiotherapy, 30 Gy is delivered as 3 Gy per fraction per day for 5 days followed by 2 days off for 10 days in total (i.e. to the same schedule as M3814).
- c Avelumab will be administered Q2W as an IV infusion over 1 hour, starting on Day 1, at a fixed dose of 800 mg in all dose levels.
- d Dose Level -1 can be evaluated upon decision of the SMC.
- e Dose Level 1 is the starting dose.

6.6.5 Dosing Instructions

6.6.5.1 Part A (M3814 + Avelumab)

M3814: A 50 mg tablet for oral administration is used during the treatment phase. The starting dose will be 100 mg BID. Subsequent doses and schedules will be determined by the SMC.

For M3814 administrations, participants will be instructed as follows:

- For all treatment days, fast at least 1 hour prior to M3814 dose and continue fasting for at least 1 hour postdose for both morning and evening M3814 dose.
- Take the prescribed dose of M3814 at approximately the same time each day.

On days with scheduled PK collection visits, the morning dose should not be taken until the participant is admitted to the clinic/hospital and the morning (predose) PK collection has been completed.

If a participant misses taking a scheduled dose of M3814, it is acceptable to take the missed dose within a window of 5 hours. If more than 5 hours has passed after the scheduled dose time, the missed dose should not be taken, and the participant should be instructed to take the next dose at the next scheduled time. Any change from dosing schedule, dose interruptions, and dose reductions should be recorded in the eCRF.

On the day of avelumab administration, M3814 can be administered at any time before or after the end of avelumab infusion at home or clinic except on the days of M3814 PK collection where M3814 should be only taken in clinic after predose PK sample has been collected.

Avelumab: will be administered Q2W as an IV infusion over 1 hour, starting on Day 1, at a fixed dose of 800 mg in all dose levels. Guidance on premedication is given in Section 6.5.5.

6.6.5.2 Part B (M3814 + Radiotherapy + Avelumab)

M3814: 50 mg tablets for oral administration is used during the treatment phase. The starting dose of M3814 in the first cohort of participants is expected to be 100 mg total daily dose, given QD (i.e. 2-fold lower than in Part A). However, this starting dose might be adjusted by the SMC based on safety, PK, and Pd data generated during the first dose level in Part A and/or emerging data from the ongoing clinical studies involving M3814. M3814 will be given starting Day 1 for 5 days/week for 2 weeks.

For M3814 administrations, participants will be instructed as follows:

- For all treatment days, fast at least 1 hour prior to M3814 dose and continue fasting for at least 1 hour postdose.
- Take the prescribed tablets of M3814 1.5 hours (± 30 minutes) before each RT fraction is started.
- On the day of avelumab treatment (Day 1), M3814 can be taken at any time after the end of avelumab infusion as long as the above conditions are met.
- On days with serial PK collection (Day 1 and Day 12), the morning dose should not be taken
 until the participant is admitted to the clinic/hospital and the morning (predose) PK collection
 has been completed.
- On the day of avelumab treatment (Day 1), M3814 can be taken at any time after the end of avelumab infusion as long as the above conditions are met.

Avelumab: to be administered Q2W as an IV infusion over 1 hour, starting on Day 1, at a fixed dose of 800 mg in all dose levels. Guidance on premedication is given in Section 6.5.5.

Radiotherapy: 3 Gy per fraction per day for 5 days a week for 2 weeks to a total dose of 30 Gy, starting Day 1 with M3814.

Multisite simultaneous RT is allowed:

- Up to 3 primary and/or metastatic lesions could be irradiated
- If more than one lesion is selected to be irradiated, symptomatic or clinically relevant primary tumors and/or metastases should be prioritized.
- All selected lesions should be irradiated the same day.

6.6.5.3 Part FE

M3814: A 50 mg tablet for oral administration is used during the treatment phase. The starting dose will be 100 mg BID. Subsequent doses and schedules will be determined based on PK and safety data.

For M3814 administrations, participants will be instructed as follows:

On Day 1 and Day 22, participants will be instructed to fast overnight for at least 8 hours followed by the meal provided at the site. M3814 should be administered within 30 minutes after the meal. The drug should be taken with approximately 240 mL (8 fluid ounces) of water. Additional water is allowed ad libitum except for 1 hour before and 1 hour after M3814 administration.

On Day 15, participants will be instructed to fast overnight for at least 8 hours followed by the M3814 administration at the site. The drug should be taken with approximately 240 mL (8 fluid ounces) of water. Additional water is allowed ad libitum except for 1 hour before and 1 hour after M3814 administration. Participants should not consume any food for at least 4 hours after the M3814 dose.

Composition of a high-fat diet: 800 to 1000 calories (protein [150 calories], carbohydrates [250 calories], fat [500 to 600 calories]). Example of high-fat diet: Two eggs fried in butter, two strips of bacon, two slices of toast with butter, four ounces of hash brown potatoes, eight ounces of whole milk

On days with scheduled PK collection visits, the morning dose should not be taken until the participant is admitted to the clinic/hospital and the morning (predose) PK collection has been completed.

If a participant misses taking a scheduled dose of M3814, it is acceptable to take the missed dose within a window of 5 hours. If more than 5 hours has passed after the scheduled dose time, the missed dose should not be taken, and the participant should be instructed to take the next dose at the next scheduled time. Any change from dosing schedule, dose interruptions, and dose reductions should be recorded in the eCRF.

On the day of avelumab administration, M3814 can be administered at any time before or after the end of avelumab infusion.

Avelumab: will be administered Q2W as an IV infusion over 1 hour, starting on Day 1, at a fixed dose of 800 mg in all dose levels. Guidance on premedication is given in Section 6.5.5.

6.6.5.4 Part A, Part B and Part FE

For M3814 administrations, participants will be instructed as follows:

- Take the assigned tablets of M3814 with a full glass of water (approximately 240 mL/8 fluid ounces).
- Swallow the tablets whole and not bite into the tablets, break them, or attempt to dissolve the
 contents in water prior to taking their assigned dose.
- If the participant vomits within 1 hour of M3814 dose, no further PK sampling should be
 performed. The participant should be given an antiemetic, but no further dose will be given that
 day. Prophylactic antiemetics should then be given prior to subsequent doses of M3814. Any
 change from dosing schedule, dose interruptions, or dose reductions should be recorded in the
 eCRF.

Each participant will stay on the avelumab assigned dose until the criteria for discontinuation are met (Section 7.1). Dosing modifications (changes in infusion rate and dose delays) as a result of AEs are described in Section 6.9.2.1. There will be no intraparticipant dose reductions for toxicity reasons.

6.6.6 Treatment Beyond Progression

6.6.6.1 Treatment Beyond Initial Progression

Participants will receive avelumab with or without M3814 in Part A and Part FE and avelumab in Part B as outlined in the Schedule of Activities (Section 1.3) until PD. Avelumab with or without M3814 in Part A and Part FE, and avelumab in Part B may continue past the initial determination of PD according to RECIST v 1.1 as long as the following criteria are met:

- Treatment with avelumab is ongoing,
- No new unacceptable treatment or disease-related toxicity,
- Tolerance of study interventions,
- Stable ECOG PS,
- Treatment beyond progression will not delay an imminent intervention to prevent serious complications of disease progression (for example, central nervous system metastases).

A radiographic assessment should be performed within 4 to 6 weeks of original PD to determine whether there has been a decrease in the tumor size, or continued PD. The assessment of clinical benefit should be balanced by clinical judgment as to whether the participant is clinically deteriorating and unlikely to receive any benefit from continued treatment with avelumab with or without M3814 in Part A and Part FE, and avelumab in Part B.

6.6.6.2 Treatment Beyond Confirmed Progression

Participants who experience PD may continue treatment with study interventions if the Investigator believes the participant will experience clinical benefit from the treatment and there

is no unacceptable toxicity resulting from the treatment. The decision to continue treatment beyond confirmed PD should be discussed with the Medical Monitor and documented in the study records.

If the participant continues with treatment after confirmed PD, they should remain on the study and continue to receive monitoring according to the Schedule of Activities (Section 1.3). Participants who continue beyond progression will be evaluated for further tumor response as per the protocol schedule.

Treatment should be discontinued permanently upon documentation of further, unequivocal, PD unless there are no alternative therapeutic options and the benefit-risk assessment is favorable in consultation between the Investigator and the Medical Monitor. In case of continuation of treatment beyond PD, treatment will be discontinued once any other criteria for withdrawal are met (see Section 7.1).

6.6.7 Continuation of Study Intervention After Local Treatment of Disease Progression

If PD is due to brain metastasis, participants may continue study interventions after the local treatment of the brain lesions with respect to the criteria defined in Section 6.5.4 and provided that the above criteria are met in addition to the following:

- Tumor assessment showing PD has been performed and was documented according to RECIST v 1.1. prior to the procedure.
- Brain metastases have been treated locally and are clinically stable for at least 2 weeks prior to reinitiation of study interventions.
- There are no ongoing neurological symptoms that are related to the brain localization of the disease (sequelae that are a consequence of the treatment of the brain metastases are acceptable).
- Participants must be either off steroids or on a stable or decreasing dose of ≤ 10 mg daily prednisone (or equivalent).
- Benefit-risk assessment to continue study intervention is favorable under consideration of any alternative treatment options as assessed by the Investigator.

In addition, if PD is mainly due to a metastatic lesion which in the opinion of the Investigator may be surgically removed, participants may continue study interventions after the local treatment of such a lesion provided that:

- Tumor assessment showing disease progression has been performed and was documented according to RECIST v 1.1. prior to the procedure.
- It has been at least 2 weeks and the participant has fully recovered from the surgery.
- Benefit-risk assessment to continue study intervention is favorable under consideration of any alternative treatment options as assessed by the Investigator.

6.7 Study Intervention After the End of the Study

After a participant has completed the study or has withdrawn early, usual treatment will be administered, if required, in accordance with the study site's standard-of-care and generally

accepted medical practice and depending on the participant's individual medical needs. The Sponsor will not provide any additional care to participants after they leave the study because such care should not differ from what is normally expected for participants with advanced malignancies.

6.8 Special Precautions

Avelumab

As a routine precaution, participants enrolled in this study must be observed for 1-hour post infusion for the first 4 infusions, in an area with resuscitation equipment and emergency agents. At all times during avelumab treatment, immediate emergency treatment of an infusion-related reaction or a severe hypersensitivity reaction according to institutional standards must be assured. In order to treat possible hypersensitivity reactions, for instance, dexamethasone 10 mg and epinephrine in a 1:1000 dilution or equivalents should always be available along with equipment for assisted ventilation.

The treatment recommendations for infusion-related reactions are outlined in Section 6.9.2.1.

Investigators should also monitor participants closely for potential irAEs, which may become manifest at any time during treatment. Such events include but are not limited to pneumonitis, hepatitis, colitis, endocrinopathies (hypothyroidism, hyperthyroidism, adrenal insufficiency, and type 1 diabetes mellitus), myocarditis, myositis, and rash. See Section 6.9.2.2 for details on the management of irAEs.

Investigators should also monitor participants closely for potential irAEs, which may become manifest earliest after weeks of treatment. Such events may consist of persistent rash, diarrhea and colitis, autoimmune hepatitis, arthritis, glomerulonephritis, cardiomyopathy, or uveitis and other inflammatory eye conditions. The spectrum of hypothetical irAEs also includes formation of auto antibodies like antinuclear antibodies or antineutrophil cytoplasmic antibodies. See Section 6.9.2.2 for details on the management of irAEs.

If a hypersensitivity reaction occurs, the participant must be treated according to the best available medical practice. Participants should be instructed to report any delayed reactions to the Investigator immediately.

M3814

In vitro studies suggest that CYP3A, CYP2C9, and CYP2C19 are involved in the metabolism of M3814. Using physiologically based PK modeling and simulation, potent inhibitors and inducers of CYP3A, CYP2C9, and CYP2C19 are predicted to have an influence on the PK of M3814. Therefore, foods (e.g. grapefruit and Seville oranges) or concomitant medications that are potent inducers or inhibitors of these enzymes should be used with caution. Participants will be instructed to avoid any intake of grapefruit, grapefruit juice, Seville oranges, Seville orange marmalade, or other products containing grapefruit or Seville oranges within 7 days before the first administration of the study intervention and during the study intervention administration.

The effect of M3814 on CYP3A-metabolized substrates is complex due to the time dependent inhibition and induction. It cannot be excluded that at high concentrations, M3814 affects the PK

of sensitive CYP3A substrates; therefore, sensitive CYP3A substrates with a narrow therapeutic index should also be used with caution and avoided if possible, during treatment with M3814. Drugs mainly metabolized by CYP2C9 with a narrow therapeutic index are to be used with caution and if possible, avoided during treatment with M3814.

The solubility of M3814 is pH dependent; therefore, antacid drugs and proton pump inhibitors might affect absorption (Section 6.5).

Drugs which are substrates of P-glycoprotein (P-gp) (e.g. dabigatran etexilate, digoxin), breast cancer resistance protein (BCRP) (e.g. rosuvastatin, sulfasalazine), or organic cation transporter 1 (OCT1) (e.g. metformin) with a narrow therapeutic index are to be used with caution. The Investigator may decide not to include a participant in the study, if the participant cannot be withdrawn from the drugs that have a narrow therapeutic index and that are known to be substrates of P-gp, BCRP, or OCT1; if the Investigator decides to enroll a participant who is treated with a drug that is known to be substrate of P-gp, BCRP, or OCT1 and has a narrow therapeutic range, close safety monitoring is advised.

The study will be performed in a study unit with direct access to a Hospital Emergency Unit. Equipment and medications, such as epinephrine and prednisolone equivalents, will be available at the study site for the treatment of emergencies.

Radiotherapy

Refer to Appendix 8 for details of RT.

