- 13. Known prior severe hypersensitivity to any of the investigational products or any component in its formulations, including known severe hypersensitivity reactions to monoclonal antibodies (NCI-CTCAE 5.0 Grade ≥ 3).

Part B only:

- 14. If the participant has symptoms of ongoing esophagitis and the treating Investigator estimates that the radiation planning target volume (PTV) will include any portion of the esophagus, the participant is not eligible unless an esophageal endoscopy rules out the presence of esophagitis.
- 15. The participant will not be eligible if more than 10% of the total esophagus volume is estimated to receive more than 15 Gy (50% of the prescribed RT dose).
- 16. If hepatic metastatic lesion is selected to be irradiated:
 - The non-tumor liver volume < 700 mL
 - Child-Pugh score ≥ 8
- 17. If the participant has an acute or chronic interstitial pulmonary disease and the treating Investigator has selected a thoracic lesion to be irradiated, the participant is not eligible.

Prior/Concomitant Therapy

18. Received:

- a. Chemotherapy, hormonal anticancer therapy with the exception of luteinizing hormone-releasing hormone analogs, biologic therapy, or any other anticancer therapy within 28 days of the first dose of study intervention administration (6 weeks for nitrosoureas or mitomycin C). For participants with rapidly growing tumors where the treating physician cannot wait for 28 days or 6 weeks, inclusion may take place if the participant meets all the other eligibility criteria and if there is no residual toxicity related to previous treatment NCI-CTCAE Grade >1.
- b. Major surgery for any reason, except diagnostic biopsy, within 4 weeks of the study intervention and/or if the participant has not fully recovered from the surgery within 4 weeks of the study intervention.
- Treatment with a live attenuated vaccine within 30 days of dosing.
- 19. Participants currently receiving (or unable to stop using prior to receiving the first dose of study intervention) medications or herbal supplements known to be strong inhibitors of CYP3A, CYP2C9, or CYP2C19 (must stop at least 1 week prior); strong inducers of CYP3A, CYP2C9, or CYP2C19 (must stop at least 3 weeks prior); or drugs mainly metabolized by CYP3A with a narrow therapeutic index (must stop at least 1 day prior).

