6.5.3 Prohibited Medicines

Prohibited medicines include those listed in the exclusion criteria (Section 5.2).

- As stated in Section 5.2, chemotherapy, hormonal anticancer therapy with the exception of
 luteinizing hormone-releasing hormone analogs, biologic therapy, or any other anticancer
 therapy within 28 days of the first dose of study intervention administration (6 weeks for
 nitrosoureas or mitomycin C). These therapies are also prohibited during the treatment period
 (Part A, Part B, and Part FE) and up to 30 days after the end of RT (Part B).
- During the treatment period (Part A, Part B, and Part FE) and up to 30 days after the end of RT (Part B), chemotherapy, extensive RT (involving ≥ 30% of bone marrow) or any other anticancer therapy (biologics or other targeted therapy or investigational agent) and antineoplastic steroid therapy are also prohibited.
- Use of any other investigational treatments, or participation in any other interventional studies, during the entire study duration (Part A, Part B, and Part FE) is not permitted.

Furthermore, the following treatments must not be administered during the study:

- Immunotherapy, immunosuppressive drugs (i.e. chemotherapy or systemic corticosteroids) except:
 - When required for the treatment of irAEs or infusion-related reactions/hypersensitivity
 - Systemic corticosteroids at physiologic doses ≤ 10 mg/day of prednisone or equivalent
 - Systemic corticosteroids for management of participants with allergy to computed tomography (CT) IV radiographic contrast media.
- Administration of a live vaccine within 30 days of study intervention.
- Growth factors (e.g. granulocyte colony stimulating factor or granulocyte macrophage colony stimulating factor). Exception: Growth factors are allowed for treatment of study intervention-related myelosuppression and for prophylaxis of repeat myelosuppression after initial occurrence.
- Herbal remedies with immunostimulating properties (for example, mistletoe extract) or known to potentially interfere with major organ function (for example, hypericin).
- Medications or herbal supplements known to be strong inhibitors or inducers of CYP3A, CYP2C9, or CYP2C19.
- Drugs mainly metabolized by CYP3A or CYP2C9 with a narrow therapeutic index as judged by the Investigator (and after optional consultation with the Sponsor; for details see Special Precautions below; Section 6.8).

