The solubility of M3814 is pH dependent; therefore, antacid drugs, H2-blocker and proton pump inhibitors (PPI) might affect absorption. PPIs should be stopped 5 days prior to the first treatment and avoided during the entire treatment period with study intervention. Antacid drugs should not be taken 1 hour before study intervention administration until 2 hours after study intervention administration. H2 blockers may be allowed but should be taken at least 2 hours after M3814 dose and stopped at least 6 hours before the next dose of M3814.

Any additional concomitant therapy that becomes necessary during the study and any change to concomitant drugs must be recorded in the corresponding section of the eCRF, noting the name, dose, duration, and indication of each drug.

If the administration of a nonpermitted concomitant drug becomes necessary during the study, e.g. because of AEs, suspension of the participant from treatment should be performed. The requirement to discontinue the participant from treatment should be discussed with the Sponsor. In case of discontinuation and where possible, the End of Treatment Visit and Safety Follow-up Visit and phone call 30 and 90 days after end of treatment should be performed as per Schedule of Activities (Table 1, Table 2, Table 3, and Table 4). Furthermore, in participants who discontinue from study intervention prior to disease progression tumor assessments should continue according to the Schedule of Activities until confirmed disease progression or start of a new anticancer treatment.

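### Section 6.8 allows potent CYP3A, CYP2C9 and CYP2C19 inhibitors and inducers with caution, although Sections 5.2 and 6.5.3 exclude and prohibit strong ones

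*Protocol*

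**What the plan says.** The M3814 part of Protocol Section 6.8 names CYP3A, CYP2C9 and CYP2C19 as enzymes involved in M3814 metabolism. It reports a modelling prediction that potent inhibitors and inducers of them influence M3814 PK. It then says, for foods and medicines in one sentence, that "concomitant medications that are potent inducers or inhibitors of these enzymes should be used with caution". The next sentence tells participants to avoid grapefruit and Seville orange products. No matching sentence follows for medicines.

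Section 5.2, criterion 19, excludes participants who take, or cannot stop, "strong inhibitors of CYP3A, CYP2C9, or CYP2C19 (must stop at least 1 week prior" or "strong inducers of CYP3A, CYP2C9, or CYP2C19 (must stop at least 3 weeks prior".

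Section 6.5.3 first carries over the medicines named in the exclusion criteria. It then gives a further list under the statement that "the following treatments must not be administered during the study". One entry reads "Medications or herbal supplements known to be strong inhibitors or inducers of CYP3A, CYP2C9, or CYP2C19". That entry has no qualifier and no reference to another section. If a nonpermitted drug becomes necessary, Section 6.5.3 says that "suspension of the participant from treatment should be performed".

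The rules for substrates with a narrow therapeutic index are looser. Criterion 19 adds "or drugs mainly metabolized by CYP3A with a narrow therapeutic index (must stop at least 1 day prior". The Section 6.5.3 list includes such drugs for CYP3A and CYP2C9, but "as judged by the Investigator (and after optional consultation with the Sponsor; for details see Special Precautions below; Section 6.8". Section 6.8 says to use both kinds with caution and avoid them if possible.

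**The concern.** An instruction to use a drug with caution permits it; an instruction that it must not be given forbids it. A site that opens Section 6.8 for guidance on interactions meets the permissive wording, with nothing there to send it back to the ban.

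Section 6.8 itself gives the reason to care: it expects these drugs to influence M3814 PK. Parts A and B assign DLTs to dose levels, and Part FE compares fed and fasted exposure. If a strong inhibitor or inducer were started on study, exposure could differ from what the nominal dose normally produces, while the DLT and PK data would still be filed under that dose. In Parts A and FE, Section 6.9.1 allows no M3814 dose reduction during the DLT or FE Assessment Period. A site acting in good faith on Section 6.8 could also create an important protocol deviation, because SAP Section 8.1 lists use of an excluded concomitant medication as one.

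**Working it through.** No arithmetic applies. The check sets the three current texts side by side.

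| Drug class | Section 5.2, criterion 19 | Section 6.5.3 | Section 6.8 |
|---|---|---|---|
| Strong or potent inhibitors | Excluded; stop 1 week ahead | Banned on study, unqualified | Caution |
| Strong or potent inducers | Excluded; stop 3 weeks ahead | Banned on study, unqualified | Caution |
| Narrow-index CYP3A substrates | Excluded; stop 1 day ahead | On the banned list, subject to Investigator judgment, refers to 6.8 | Caution, avoid if possible |

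1. *Same enzymes?* Yes. The enzymes meant in Section 6.8 are the three named just before: CYP3A, CYP2C9 and CYP2C19. Criterion 19 and Section 6.5.3 name the same three.

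2. *Same drugs?* Section 6.8 says potent; the other two sections say strong. The protocol defines no potent category distinct from strong. If potent were meant more widely, it would still include the strong agents. The overlap exists on either reading.

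3. *Same period?* Criterion 19 governs entry, and Section 6.5.3 governs the time on study. Section 6.8 states no period for medicines, so it overlaps both.

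4. *Does Section 6.8 resolve the conflict itself?* For the named foods, yes: the following sentence turns caution into avoidance. For medicines, no. The text does not limit caution to moderate agents and does not refer to Section 5.2 or to the ban in Section 6.5.3.

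5. *Narrow-index CYP3A substrates.* Criterion 19 excludes them without a qualifier. The Section 6.5.3 entry defers to Investigator judgment and refers to Section 6.8 for details, so those two sections can largely be read together. What remains open is whether a drug barred at entry may be started on study with caution. Matching the terms also needs an assumption, because Section 6.8 speaks of sensitive CYP3A substrates and the other sections of drugs mainly metabolized by CYP3A.

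6. *Size.* An effect on the DLT rate or PK would need the frequency of such co-medication and the resulting change in exposure. The documents give neither, so no estimate is made.

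**The case against.** The best defence is that the protocol as a whole leaves little doubt about the rule. Section 5 does not permit waivers of the eligibility criteria. Section 6.5.2 permits only medicines that the protocol does not exclude, so Section 6.8 cannot create a permission. Section 6.5.3 says what to do when a nonpermitted drug is needed, and SAP Section 8.1 treats the use as an important deviation. Section 6.5.2 also allows any medicine needed in an emergency, even at the cost of a deviation, and advice to take care has a use there. All of this stands and limits the practical risk. A careful site would probably follow the stricter rule.

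It does not remove the conflict. The caution in Section 6.8 is general and is not confined to emergencies. A reader has to combine several sections to learn that a direct instruction in this one does not apply.

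A reader might also infer that the current amendment's summary of changes shows the caution wording was left behind by mistake, because it lists Section 6.8 beside the new ban on CYP2C9 inhibitors and inducers. The documents do not support that inference. The same row adds caution for CYP2C9 substrates, which by itself can explain why Section 6.8 is listed.

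**Conclusion.** The inconsistency is real and minor. For strong inhibitors and inducers of CYP3A, CYP2C9 and CYP2C19, Section 6.8 gives a permissive instruction where Sections 5.2 and 6.5.3 exclude and ban. It matters mainly for drugs started on study. The conclusion rests on potent in Section 6.8 meaning, or at least including, strong. Confidence is high for this class. The position on narrow-index CYP3A substrates is less clear and calls for a question to the sponsor.

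Three stronger readings are tempting but not supported:

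- *Section 6.8 sets a rival handling rule under which both drugs continue and the participant stays evaluable for DLT.* Section 6.8 says nothing on continuing, suspending or evaluability. Nor can the number of missable M3814 doses measure the conflict: Section 6.5.3 gives no length of suspension, and Section 6.6.1 also requires every planned avelumab dose.
- *Sections 6.5.3 and 6.8 refer to each other in a circle.* The reference runs one way on CYP drugs. The only return reference in the M3814 text of Section 6.8, to Section 6.5, concerns antacids and proton pump inhibitors.
- *Narrow-index CYP2C9 substrates should come off the Section 6.5.3 list.* That would loosen a safety restriction on the strength of an amendment rationale that is partly redacted, without sight of the interaction data.

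**What to change.** In Section 6.8, keep the food instruction and replace the medicine wording with:

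*Strong (potent) inhibitors and inducers of CYP3A, CYP2C9 and CYP2C19 are prohibited per Section 5.2 criterion 19 and Section 6.5.3; stop inhibitors at least 1 week and inducers at least 3 weeks before the first dose.*

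For narrow-index CYP3A substrates, ask the sponsor to confirm which on-study rule is intended: the ban that criterion 19 implies, or use at the Investigator's discretion with caution. This is a clinical choice, and the review should not make it. Leave the CYP2C9 substrate text as it is.

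The cost is one wording change at the next amendment. It adds no visits, data, entry exclusions or washout periods and needs no SAP change. The emergency provision in Section 6.5.2 is untouched.
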